7.14 Other Data Summaries

Not applicable

7.15 Changes in Analysis Methods Specified in the Protocol

The following changes were made to the methods specified in the protocol:

- For the Modified Bates- Jensen Wound Assessment Tool, instead of using a t-test to test for a difference between treatments in the total score at 12 weeks, the repeated measures ANOVA model which was already being used will also be used to

CONFIDENTIAL AND PROPRIETARY

This document contains information that is confidential and proprietary to Smith & Nephew PLC and Smith & Nephew, Inc. and is intended for use only by Smith & Nephew and its manufacturer. It shall not be reproduced or copied in whole or in part, nor shall the contents be disclosed by any means without prior written permission from Smith & Nephew, nor shall anyone make any use of it that is contrary to the expressed or implied wishes of Smith & Nephew

Statistical Analysis Plan	 smith&nephew
A Pilot Randomized Controlled Trial to Evaluate an Advanced Borderless Dressing (ALLEVYN™ LIFE Non-Bordered) in the Treatment of Chronic Ulcers	Number: CT1603ALF
	ST: 1005
	Version: 1.0, 27-Jul-2018
	Page: 27 of 27

estimate the difference in least squares mean (LSMean) between treatments at the 12 week visit along with associated 95% confidence interval.

- The number of serious device-related adverse events is expected to be low, so it would not be useful to calculate the 1-sided upper 95% CI as originally planned in the protocol. Instead the number will be summarised and the individual cases will be listed.

CONFIDENTIAL AND PROPRIETARY

This document contains information that is confidential and proprietary to Smith & Nephew PLC and Smith & Nephew, Inc. and is intended for use only by Smith & Nephew and its manufacturer. It shall not be reproduced or copied in whole or in part, nor shall the contents be disclosed by any means without prior written permission from Smith & Nephew, nor shall anyone make any use of it that is contrary to the expressed or implied wishes of Smith & Nephew

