#### **4.2.2 Hazards/Harms**

This will be the first study to evaluate the use of ALNB in clinical practice; there is currently no direct clinical evidence concerning the safety of ALNB.

ALLEVYN LIFE has been used widely over the last four years and has been shown to be equivalent to ALNB with regard to materials and fluid handling properties (see Section 6).

Published clinical studies with ALLEVYN LIFE, risk management reports, and post-marketing

surveillance (PMS) data consistently indicate that the risk of adverse events is low and that reactions which do occur are generally local to the application site and are mild in severity. Adverse events are well characterized and are manageable in the majority of cases. As such, ALLEVYN LIFE demonstrates an acceptable benefit-risk profile.

Because of the similarities between ALLEVYN LIFE and ALNB, the anticipated medical benefits of ALNB are also expected to outweigh risks. There are some differences between the two products, including:

- ALNB can be cut to size without compromising its performance characteristics
- ALNB does not incorporate a change indicator, as this would be obscured by any secondary dressing
- ALNB includes a lower tack adhesive, to serve as a ‘third hand’, and enable the dressing to be removed and repositioned more easily
- ALNB requires the use of a secondary dressing to aid retention

The use of a lower tack adhesive with ALNB may positively impact safety by lowering the incidence and severity of skin stripping resulting from its use. Unlike ALLEVYN LIFE, ALNB requires a secondary dressing to aid retention. Choice of ancillary dressing, together with associated risks relating to this secondary device, will be carefully monitored during this study.

There are no anticipated Serious Adverse Device Effects (SADE) associated with the use of ALNB.

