### **8.3 METHODS USED TO MINIMIZE BIAS**

Blinding of subjects and HCP to treatment allocation is not possible due to obvious physical differences in the appearance of dressings and sterile packaging. Bias reduction will consist of subjects randomly allocated to the two groups, ALNB and SC, to control for the influence of extraneous variables on treatment outcomes. In this way, no Investigator will be able to direct a particular subject to a particular treatment. Baseline procedures and assessments are performed prior to assigning the subject to a treatment group. SC was selected as the comparator treatment, rather than a specific competitor dressing, together with the recruitment of subjects from multiple treatment facilities to widen the generalizability of results to normal clinical practice.

Unequal allocation of subjects in favor of ALNB will ensure that twenty-five (25) subjects receive treatment with ALNB, which is viewed as a reasonable minimum requirement in providing basic safety data for the primary dressing of interest. Additionally, treatment allocation will be stratified by ulcer type to safeguard against major imbalances in clinical characteristics at baseline and aid comparability between groups.

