### Adverse Events

Adverse events will be coded and grouped by system organ class using the Dictionary for Medical Drug Regulatory Activities (MedDRA).

The number of subjects reporting: adverse events, serious adverse events, severe adverse events, device-related adverse events, serious device-related adverse events, unexpected adverse events, and serious unexpected adverse events will be summarized. In addition, for each adverse event, the following will be summarized: severity, treatment, the relationship to the investigational device, the possible cause if related, outcome and duration of the resolved adverse events and the duration of the adverse events at trial discontinuation.

The proportion of subjects with a device-related adverse event will be compared between treatments using Fisher's exact test. In addition, the percentage of serious device-related adverse events and the corresponding 1-sided upper 95% confidence limit will be detailed assuming a Poisson distribution for serious device-related adverse events separately for each treatment.

The number and proportion of subjects reporting treatment-emergent adverse events split by treatment separately by system organ class and preferred term will be summarized by:

1. Their relationship with the investigational device (not related or related). If the relationship is missing, the adverse event will be assumed to be treatment-related and a footnote will be added to the table. If a subject experiences more than one preferred term within a system organ class, then the relationship at the system organ class level for that subject will be reported according to their most related relationship for each preferred term.
2. The severity of the adverse event (mild, moderate or severe).

3. Whether or not the adverse event is serious
4. The adverse event outcome.
5. Whether or not the adverse event is expected or unexpected.

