## **11. SAMPLE SIZE JUSTIFICATION**

Since there is no previous data upon which to base a sample size calculation, no statistical justification for the sample size is provided. Twenty-five (25) subjects were desired for the ALNB group; a 5:3 randomization ratio was selected so that approximately forty (40) subjects would be enrolled into the study. This number of subjects is based on feasibility only.

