7.13 Analysis of Safety Endpoints

All safety analyses and summaries will be conducted using the Safety Population. Unless otherwise stated, all safety summaries will be presented by treatment and overall.

Extent of Exposure

The duration of treatment will be summarized by treatment and overall using descriptive summary characteristics for continuous data.

Adverse Events

Adverse events will be coded and grouped by system organ class using a recent version of the Dictionary for Medical Drug Regulatory Activities (MedDRA).

The number of subjects reporting: adverse events, serious adverse events, severe adverse events, device-related adverse events, serious device-related adverse events, unexpected adverse events, and serious unexpected adverse events will be summarized. In addition, for each adverse event, the following will be summarized: severity, treatment, the relationship to the investigational device, outcome and duration of the resolved adverse events and the duration of the adverse events at trial discontinuation.

The proportion of subjects with a device-related adverse event will be compared between treatments using Fisher's exact test.

The number and proportion of subjects reporting treatment-related adverse, by system organ class and preferred term will be summarized by treatment and overall for:

CONFIDENTIAL AND PROPRIETARY

This document contains information that is confidential and proprietary to Smith & Nephew PLC and Smith & Nephew, Inc. and is intended for use only by Smith & Nephew and its manufacturer. It shall not be reproduced or copied in whole or in part, nor shall the contents be disclosed by any means without prior written permission from Smith & Nephew, nor shall anyone make any use of it that is contrary to the expressed or implied wishes of Smith & Nephew

Statistical Analysis Plan	 Number: CT1603ALF ST: 1005 Version: 1.0, 27-Jul-2018 Page: 26 of 27
A Pilot Randomized Controlled Trial to Evaluate an Advanced Borderless Dressing (ALLEVYN™ LIFE Non-Bordered) in the Treatment of Chronic Ulcers	

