1. Their relationship with the investigational device (not related or related). If the relationship is missing, the adverse event will be assumed to be treatment-related and a footnote will be added to the table. If a subject experiences more than one preferred term within a system organ class, then the relationship at the system organ class level for that subject will be reported according to their most related (or worse) relationship for each preferred term.
2. The severity of the adverse event (mild, moderate or severe). If a subject experiences more than one preferred term within a system organ class, then the severity at the system organ class level for that subject will be reported according to their worst severity for each preferred term.
3. Whether or not the adverse event is serious
4. The adverse event outcome.
5. Whether or not the adverse event is expected or unexpected.

Device deficiencies

The number of device deficiencies and the number of patients reporting a device deficiency will be summarized.

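### The SAP drops the upper confidence limit for serious device-related adverse events because few are expected, which is when the limit is most needed; two related safety wordings also need reconciling

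*SAP*

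**What the plan says.** Protocol 10.3 (Adverse Events) states that, separately for each treatment, "the percentage of serious device-related adverse events and the corresponding 1-sided upper 95% confidence limit will be detailed assuming a Poisson distribution". SAP 7.15 lists a departure from this: the number of such events is expected to be low, "so it would not be useful to calculate the 1-sided upper 95% CI as originally planned in the protocol". The number will be summarised and the cases listed. SAP 7.13 gives no other interval for these events; its Fisher's exact test concerns all device-related events, serious or not.

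On what the trial is meant to show about safety, Protocol 4.2.2 says that "there is currently no direct clinical evidence concerning the safety of ALNB". Protocol 8.3 defends the unequal allocation because it secures 25 ALNB subjects, "which is viewed as a reasonable minimum requirement in providing basic safety data for the primary dressing of interest". Protocol 11 says of the total that "This number of subjects is based on feasibility only".

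Two further wordings bear on the same outputs:

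- **Scope of the system organ class and preferred term tables.** The protocol has "The number and proportion of subjects reporting treatment-emergent adverse events split by treatment separately by system organ class". SAP 7.13 has "The number and proportion of subjects reporting treatment-related adverse, by system organ class and preferred term will be summarized", with a noun missing. Item 1 beneath that sentence still splits the table by "Their relationship with the investigational device (not related or related").
- **Meaning of device-related.** Protocol 12.1.2 counts an event related to either the investigational or the comparator device, and adds events related to the sponsor's ancillary products. The SAP 7.4 flags name the investigational device only, as does some wording in Protocol 10.3. SAP 7.13 does not say which definition its Fisher's test uses.

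**The concern.** A low expected count is not a reason to omit an upper limit. The exact limit is defined at zero events, and with zero or one event the point estimate says least about the risk that remains possible. The low expectation was not new either: the protocol that planned the limit already says in 4.2.2 that no serious adverse device effects are anticipated.

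If no serious device-related event occurs, the report will show a zero and an empty listing, with nothing on the risk still compatible with the data. For a dressing without direct clinical safety data, in a trial whose ALNB arm was sized with basic safety data in mind, that is the main safety statement the sample could support.

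Of the two wordings, the first, read literally, would remove unrelated events from the system organ class and preferred term breakdowns, though not from the overall counts. The second could put SC at or near zero in the between-arm comparison because of how the flag is built rather than what happened to subjects.

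**Working it through.** **Inputs.** Arm sizes are from the protocol synopsis: 25 ALNB and 15 SC. They follow from 40 subjects at 5:3, since 40 × 5/8 = 25 and 40 × 3/8 = 15. The denominator is the Safety Population, taken here as every planned subject treated. The documents give no event rate and no numerical limit, so there is no stated figure to reproduce beyond the arm sizes.

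**Formulas**, for x events (Poisson) or x subjects with an event (binomial) and n treated subjects:

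- Poisson one-sided 95% upper limit = χ²(0.95; 2(x+1) df) / (2n)
- Exact binomial (Clopper-Pearson) one-sided 95% upper limit = 0.95 quantile of Beta(x+1, n−x)

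At x = 0 the Poisson numerator is χ²(0.95; 2)/2 = 2.996, giving 2.996/25 = 12.0% and 2.996/15 = 20.0%. The binomial limit is 1 − 0.05^(1/n), giving 11.3% and 18.1%.

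| Observed | Poisson | Exact binomial |
|---|---|---|
| ALNB 0/25 | 12.0% | 11.3% |
| ALNB 1/25 | 19.0% | 17.6% |
| ALNB 2/25 | 25.2% | 23.1% |
| SC 0/15 | 20.0% | 18.1% |
| SC 1/15 | 31.6% | 27.9% |
| SC 2/15 | 42.0% | 36.3% |

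With an assumed smaller Safety Population of 20 and 12, the zero-event Poisson limits rise to 15.0% and 25.0%.

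**How much a zero tells us.** The chance of no affected subject among 25 is (1 − p)^25. For assumed true rates p:

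- 1%: 77.8%
- 2%: 60.3%
- 5%: 27.7%
- 10%: 7.2%

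Zero in 25 is therefore an unremarkable result even at a true rate of 5%.

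**The table wording.** A split into related and not related has no content if only related events enter the table. SAP 7.13 therefore contradicts itself. SAP 7.15 does not list the narrower scope as a change, so a drafting slip is the likely explanation.

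**The device-related flag.** SAP 7.4 is the only derivation given. If it is used, an event attributed to an SC dressing does not count, while the same event attributed to ALNB does. To show the possible effect, two-sided Fisher p-values for assumed counts are:

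| ALNB | SC | p |
|---|---|---|
| 5/25 | 0/15 | 0.137 |
| 6/25 | 0/15 | 0.067 |
| 7/25 | 0/15 | 0.033 |
| 7/25 | 1/15 | 0.219 |
| 7/25 | 2/15 | 0.440 |

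At 7/25, whether one or two comparator-related events are counted moves the result across the 5% level.

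**The case against.** The change is disclosed in the section meant for it, with its reason. Nothing in either document turns on the limit: this is a pilot sized on feasibility, with descriptive safety reporting, and a reader who has the count and the arm size can work out the bound. The expectation of few events has a basis, since Protocol 4.2.2 cites four years of wide use of the related dressing, describes its risk as low, and anticipates no serious device effects. The table wording is close to editorial. The flag matters only if it feeds Fisher's test, and SAP 7.13 says device-related without restricting it to the investigational device. The figure of 7/25 is the smallest ALNB count that is significant against 0/15; at 5/25 even a zero on SC would not give significance.

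Most of this is accurate and bears on weight. It shows that this is lost information with a poor rationale, not concealment or a biased primary result. It does not rescue the rationale: an expectation of few events borrowed from a related product is a reason to show what the new data can exclude. A derivable bound is also not a reported one, and at zero events the promised listing is empty. One part of the objection shapes the remedy: the protocol's Poisson wording leaves the numerator and denominator implicit, so a reinstated limit must state them.

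**Conclusion.** The concern holds. It should be corrected, but it does not affect the primary analysis. With zero serious device-related events, the data would remain compatible with rates up to about 11% to 12% on ALNB and 18% to 20% on SC, and the current SAP would report neither. These figures assume that all 25 and 15 planned subjects are treated; fewer treated subjects widen them. The table wording is probably a slip, and its literal effect is confined to the breakdown tables. The definition problem is conditional: it arises if the SAP 7.4 flag is used in Fisher's test and disappears if the Protocol 12.1.2 definition is used. The Fisher p-values illustrate sensitivity and do not predict event rates.

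**What to change.** - **SAP 7.13:** reinstate, for each treatment in the Safety Population, the one-sided 95% upper limit for serious device-related adverse events, reported even when none is observed. Keep the protocol's Poisson limit, stating that it is events over treated subjects, and delete the SAP 7.15 bullet. If an exact binomial limit on subjects with at least one such event is preferred, rewrite that bullet to declare the change of method and unit.
- **SAP 7.13, table sentence:** replace treatment-related with treatment-emergent and restore the missing noun.
- **SAP 7.4:** derive the device-related flags in both arms by the Protocol 12.1.2 definition, covering the investigational or comparator device and the sponsor's ancillary products. State in 7.13 that Fisher's test uses the resulting device-related flag.

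The cost is SAP wording and a few lines of code, with no new data. The sponsor also accepts a figure that looks less favourable than a plain zero.
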